4.2 Rationale for the Proposed Trial

The rationale for administration of HIL-214 to infants 4 months (+7 days) of age at the time of initial trial vaccine administration is based on epidemiological data which shows that the risk of norovirus AGE increases in infants aged ~6 months old [14]; the rationale for inclusion of infants 2 months (+28 days) of age at enrolment is that infants also receive the required routine childhood vaccines in the participating countries at this age as per national guidelines.

This phase 2 trial aims to evaluate the immune response to routine pediatric vaccines (diphtheria [DT] and tetanus toxoid [TT] and acellular pertussis [aP] adsorbed, hepatitis B [HepB], inactivated polio vaccine [IPV], and *Haemophilus influenzae* type b [Hib] or DTaP-Hib-IPV-HepB, rotavirus [RV1], and pneumococcal conjugate [PCV13] vaccines) when co-administered with HIL-214 at 4 and 6 months of age, compared to that of the routine pediatric vaccines co-administered with placebo. Infants will be enrolled at the age of 2 months (+28 days) and will receive their routine childhood vaccines as part of the trial at 2, 4 and 6 months of age. HIL-214 will be administered as a 2-dose regimen, the first one when the child is 4 months of age and the second one when the child is 6 months of age, concomitantly with routine pediatric vaccines. The second trial arm will receive the routine childhood vaccines, co-administered with placebo at the age of 4 and 6 months. A placebo arm is included to allow an unbiased evaluation of the immunogenicity and safety of HIL-214 when administered with routine pediatric vaccines. A target number of at least 100 subjects will be recruited in the US to obtain co-administration data for this population. This trial is designed to support the concomitant administration of routine pediatric vaccines during the planned phase 3 HIL-214 efficacy trial.

This phase 2 trial will be conducted in accordance with the protocol, International Council for Harmonisation of Technical Requirements for Pharmaceuticals for Human Use (ICH) and Good Clinical Practice (GCP) Guidelines, and applicable regulatory requirements [2].

CONFIDENTIAL

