5.2 Randomisation and Blinding

Up to 400 subjects (infants aged 2 months [+14 days]) will be enrolled and randomized (1:1) to two arms by interactive response technology (IRT):

- Arm 1 (N=200): HIL-214 (1 dose at 4 months of age and 1 dose at 6 months of age) and routine childhood vaccines according to schedule.
- Arm 2 (N=200): Placebo (1 dose at 4 months of age and 1 dose at 6 months of age) and routine childhood vaccines according to schedule.

The investigator or investigator's designee will access the IRT on Visit 1 to obtain the subject number.

The investigator or investigator's designee will utilize the IRT to randomize all subjects into either the HIL-214 or placebo arms at Visit 2. During this contact, the investigator or designee will provide the necessary subject identifying information. Randomization will be stratified by country.

Randomization information will be stored in a secured area, accessible only by authorized personnel.

The subjects, data collectors (e.g., investigator) and data evaluators are blinded to the material administered.

Trial vaccine administration must be done by designated unblinded site staff, in which the trial vaccine is selected using the subject's number. The designated unblinded site staff must not be involved with data collection of any sort including safety evaluation of the subject after administration of the trial vaccine.

The trial blind shall not be broken by the investigator unless information concerning HIL-214 is necessary for the medical treatment of a subject. In the event of a medical emergency, if possible, the medical monitor should be contacted before the trial blind is broken to discuss the need for unblinding. For unblinding a subject, the trial vaccine assignment will be obtained by the investigator, by accessing the IRT.

If any subject is unblinded, the subject must be withdrawn from the trial and their data no longer evaluated.

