5.4.2 Geometric Mean

The geometric mean (GM) of a set of numbers x_1, x_2, \dots, x_N is calculated by taking the exponential of the mean of the logged values, as per the following formula

$$GM_x = \exp \left\{ \frac{\sum_{i=1}^N \ln(x_i)}{N} \right\}.$$

The geometric standard deviation (GSD) for the same set of numbers is given by

$$GSD_x = \exp \left\{ \sqrt{\frac{\sum_{i=1}^n \left(\ln \left(\frac{x_i}{GM_x} \right) \right)^2}{n}} \right\}.$$

The 95% confidence interval (CI) is calculated as per the following formula:

$$95\% CI = \exp \left\{ \ln(GM) \pm Z_{1-\frac{\alpha}{2}} \frac{\ln(GSD)}{\sqrt{n}} \right\}$$

where α is the selected level of confidence. All confidence intervals outlined in this SAP will be two sided 95% confidence intervals, i.e. with $\alpha = 0.05$.

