5.4.3 Geometric Mean Ratio

The geometric mean ratio (GMR) is the ratio of two different geometric means (Section Error! Reference source not found.). The GMR and corresponding 95% CI will be calculated using an analysis of variance model (ANOVA). The difference between the natural logarithm of the values and 95% CI will be calculated, with the exponential of these values being the GMR and corresponding 95% CI.

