5.4.4 Geometric Mean Fold Rise

The geometric mean fold rise (GMFR) is given by taking the mean of the natural logarithm of the fold increases (**Section 5.3.2.1**). Therefore for the fold increases fi_1, \dots, fi_n , the GMFR is

$$GMFR = \exp \sum_{j=1}^n (\log\{fi_j\} / n).$$

Which is equivalent to

$$GMFR = \frac{GM_4}{GM_2}$$

where GM_2 is the geometric mean at Visit 2 and GM_4 is the geometric mean at Visit 4.

The 95% confidence interval for GMFR will be calculated using the same method as the 95% CI for GM (outlined in **Section 5.4.2**) but using the log of the fold rises rather than the log of concentrations.

6 Sample Size

This trial is designed to be descriptive, and therefore the sample size was not determined based on formal statistical power calculations. The planned number of subjects is approximately 400, with 200 receiving HIL-214 and routine childhood vaccines and 200 receiving Placebo and routine childhood vaccines.

7 General Considerations

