7.1 Analysis Sets

For the purposes of analysis, the subject analysis sets are defined in **Table 3**.

Table 3: Subject Analysis Sets

Subject Analysis Set	Description
Enrolled analysis set	
• All subjects who signed the informed consent
Randomized analysis set	
• All subjects in the enrolled analysis set that were randomized
Immunogenicity evaluable analysis set	
• All subjects in the randomized analysis set that receive all doses of all study vaccines (routine and trial vaccines) within the required time window*
Immunogenicity full analysis set	
• All subjects in the randomized analysis set that receive at least one dose of a trial vaccine within the required time window*
Safety analysis set	
• All subjects in the randomized analysis set who are exposed to the trial vaccine. Subjects will be included in the analyses according to the trial vaccine (HIL-214 or Placebo) they actually received

*This window will be defined at the blinded data review meeting (BDRM)

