For continuous variables the ANOVA models will include all non-missing data for the parameter of interest and then the weights to account for the missing data. For binary data the proportions, which will be calculated on the complete cases data, will be reweighted, and the reweighted proportions will be used in the calculation of the confidence intervals. Therefore, in Equation (1) in [Section 5.4.1](#) will be calculated as the following:

$$\text{Difference in percentage} = (p_2 - p_1) * 100 = \left(\frac{(E_3|t_3 \times w_3) + (E_4|t_4 \times w_4)}{N_2} - \frac{(E_1|t_1 \times w_1) + (E_2|t_2 \times w_2)}{N_1} \right) * 100$$

Where E_i are the number of observed events in each category t_i and N_1 and N_2 are the number of subjects in the analysis set in the placebo and vaccine groups respectively. If all observed cases are positive in both vaccine groups, then the difference will be set to 0.

Equation (2) in [Section 5.4.1](#) will be calculated as the following:

$$\text{MN CI} = \left((\hat{p}_2 - \hat{p}_1) \pm Z_{1-\frac{\alpha}{2}} \sqrt{\lambda \left(\frac{\tilde{p}_2(1-\tilde{p}_2)}{N_2} + \frac{\tilde{p}_1(1-\tilde{p}_1)}{N_1} \right)} \right) * 100$$

Where $\lambda = \frac{N_1+N_2}{N_1+N_2-1}$.

If all observed cases are positive in both vaccine groups confidence intervals will not be calculated.

In the tables the number of events will be rounded to the nearest integer value and Clopper-Pearson CIs will be calculated using the exact weight-adjusted values using the Beta distribution. If all observed cases are positive the number of events will be set to N_1 and N_2 and these values will be used to calculate the confidence intervals.

If insufficient non-missing data are collected in participants with 1 trial vaccination the vaccine groups will be pooled to give the following vaccine options:

- Placebo vaccinations only (t_1)
- At least one HIL-214 vaccination (t_2)

The above formulae will be adjusted accordingly.

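### The supplementary GMR intervals come from an inverse-probability-weighted ANOVA with no variance estimator suited to such weights, so they are too narrow if only a low fraction of a sizeable one-dose group has a Visit 4 sample

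*SAP*

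**What the plan says.** The supplementary estimands use the immunogenicity full analysis set: randomized infants "that receive at least one dose of a trial vaccine within the required time window" (SAP 7.1). Infants with only one trial dose therefore belong to it.

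SAP 7.5.1 models the probability of complete data by logistic regression on one four-level factor (placebo or HIL-214, one or two doses). The weight is the inverse of that probability. For continuous endpoints, "the ANOVA models will include all non-missing data for the parameter of interest and then the weights to account for the missing data". SAP 5.4.3 adds: "The GMR and corresponding 95% CI will be calculated using an analysis of variance model (ANOVA"). SAP 9.1.1.3 repeats this and refers to 7.5.1 for the supplementary estimands. SAP 12 names SAS, but no procedure, robust option or bootstrap.

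SAP 7.5.1 also pools the one- and two-dose groups within each arm if too few non-missing data are collected in one-dose infants. It does not say how few. The SAP amendment table gives the reason as cells with a count of 0.

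**The concern.** A weighted ANOVA, unless told otherwise, treats its weights as statements about precision: an observation with weight 5 counts as if its variance were one fifth of the common value. Inverse-probability weights mean something else. A weight of 5 says that one sampled infant stands in for five, while that infant's result is as variable as anyone's. The point estimate is the intended one, but the model-based standard error is not.

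The two agree when weights are equal within an arm and diverge when they differ. Weights become unequal if one-dose infants often lack a Visit 4 sample. That is plausible, because an infant withdrawn between Visits 2 and 3 has one dose and no later blood draw. The trial is descriptive ("the sample size was not determined based on formal statistical power calculations"), so the intervals are its main inferential output. At stake is whether the supplementary 95% CIs for the pertussis, pneumococcal and RV1 GMRs have their stated coverage.

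**Working it through.** The plan states no CI width or variance for this analysis, so there is no figure to reproduce.

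**Inputs from the documents**
- Arm size: "with 200 receiving HIL-214 and routine childhood vaccines and 200 receiving Placebo and routine childhood vaccines" (SAP 6), allocated 1:1 (SAP 5.2).
- US subset: "A target number of at least 100 subjects will be recruited in the US" (Protocol 4.2), so about 50 per arm at the minimum.
- Interval: "All confidence intervals outlined in this SAP will be two sided 95% confidence intervals" (SAP 5.4.2).
- Continuous primary endpoints: 3 pertussis + 13 pneumococcal + 1 RV1 = 17 (SAP 9.1.1.2).

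**Assumptions, not in the documents:** the number of one-dose infants, the number of them sampled at Visit 4, about 95% of two-dose infants sampled, the same SD σ of log concentration in all cells, no difference in mean by dose, the same pattern in both arms, and no country term.

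**Formulas.** The weight model is saturated, so the weight in cell h is N_h/n_h (cell size over number sampled). In an arm with N infants, of whom n are sampled:
- Sum of weights = N, and sum of squared weights = Σ N_h²/n_h.
- Model-based variance of the arm mean = MSE/Σw, which is close to σ²/n.
- Actual variance of the weighted mean = σ² Σw²/(Σw)² = σ²/n_eff, with n_eff = (Σw)²/Σw².
- Model SE / actual SE = sqrt(n_eff/n) = 1/sqrt(1 + CV² of the weights).
- Approximate coverage = 2Φ(1.96 × SE ratio) − 1.

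**Worked case:** 190 two-dose infants (181 sampled) and 10 one-dose infants (2 sampled).
- Weights: 190/181 = 1.050 and 10/2 = 5.
- Σw² = 190²/181 + 10²/2 = 199.45 + 50 = 249.45.
- n_eff = 200²/249.45 = 160.4, against n = 183 used by the model.
- SE ratio = sqrt(160.4/183) = 0.936, so the SE is 6.4% too small.
- Coverage = 2Φ(1.96 × 0.936) − 1 = 93.3%.

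| Two-dose: total/sampled | One-dose: total/sampled | n | n_eff | SE ratio | Coverage (formula) | Coverage (simulated) |
|---|---|---|---|---|---|---|
| 190/181 | 10/2 | 183 | 160.4 | 0.936 | 93.3% | 93.3% |
| 180/171 | 20/5 | 176 | 148.4 | 0.918 | 92.8% | 93.0% |
| 185/176 | 15/2 | 178 | 130.3 | 0.856 | 90.7% | 90.4% |
| 46/44 (US size) | 4/1 | 45 | 39.0 | 0.931 | 93.2% | 93.3% |
| 195/185 | 5/2 | 187 | 183.5 | 0.990 | 94.8% | not run |
| 190/181 | 10/8 | 189 | 188.7 | 0.999 | 95.0% | 95.0% |

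The simulated column fixes the counts shown. The formula gives shortfalls of 6.4%, 8.2% and 14.4% for the first three rows; simulation gave 6%, 8 to 9% and 15%.

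**What drives it.** It is the sampled fraction together with the size of the one-dose group. Two sampled infants cost 1% of the SE when they stand for 5, but 14% when they stand for 15.

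**Check of the remedy.** A further simulation (8,000 trials per setting, 200 per arm, weights re-estimated each time, pooling only when a one-dose cell had no sample) compared the model-based CI with a sandwich CI:
- 10% one-dose, 30% of them sampled: coverage 92.7% against 94.6%; the sandwich CI is 1.08 times as wide.
- 10% one-dose, 10% sampled: 88.3% against 94.8%; 1.21 times as wide.
- 5% one-dose, 30% sampled: 92.9% against 94.1%; 1.04 times as wide.
- 2.5% one-dose: practically no difference.

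Monte Carlo error is about ±0.5 points. If one-dose means are 1 SD lower, the sandwich CI covers about 95 to 96%, so it is slightly conservative.

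**The case against.** **Pooling.** The strongest reply is that the SAP already guards against sparse one-dose cells. Once dose groups are pooled, weights are constant within an arm and the effect goes: with pooling, simulated coverage was 95.2% (2 of 10), 95.0% (2 of 15) and 94.8% (1 of 4, US size). This stands as a limit on the point. It does not dispose of it, because the trigger has no number and its stated reason covers only empty cells. A cell with 1 to 5 sampled infants can go unpooled.

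**Adverse counts.** The low sampling fractions are assumed. Protocol 7.5 asks for all efforts to continue immunogenicity collection after vaccine discontinuation, and Protocol 10.4.1 asks for attempts to obtain remaining blood samples. If these succeed, the error is negligible. That too stands, and is why the size is given as a range.

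**Silence is not a prescription.** A reader might infer that the SAP orders the weights to be used as precision weights. It does not; that is the default behaviour of the analysis it describes. A robust variance is not excluded, but it has to be stated to be part of the plan.

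**Stakes.** A reader might also infer that the trial's only treatment-policy result is compromised. The documents do not support this: the safety, supplementary binary and supplementary secondary analyses also use treatment policy for schedule non-compliance. The primary GMRs are unweighted complete-case estimates, and no margin or success rule depends on the supplementary intervals.

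**Conclusion.** The point holds, conditionally. As written, the supplementary GMR intervals come from a weighted ANOVA without a variance estimator that suits the weights. The ordinary interval is too narrow when a low fraction of a one-dose group that is not tiny has a Visit 4 sample and the groups are not pooled. In arms of 200, under the assumed adverse counts, the SE is about 6 to 15% too small and coverage falls to between about 93% and 90%. It would be too strong to say that the intervals are too narrow whenever few one-dose infants are sampled: with 2 of 5 sampled the error is 1%.

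The scenarios with 200 per arm apply to the overall pneumococcal and RV1 analyses, and only approximately, since those models also carry country. The pertussis endpoints are analysed by country only (SAP 7.4), in smaller groups. The sizes rest on equal variances and no dose effect; a lower one-dose mean reduces the error slightly. The concern is confined to the supplementary GMR intervals of the 17 continuous primary endpoints.

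**What to change.** Make two additions to SAP 7.5.1 before unblinding:

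1. State that CIs from the weighted ANOVA use a robust (sandwich) variance, preferably with a small-sample correction such as HC3, or a bootstrap that re-estimates the weights in each resample.
2. Give a numeric minimum of sampled one-dose infants, for each arm and analysis group (overall or country), below which the dose groups are pooled.

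A contrast of the four cell means, weighted by cell size, is a possible alternative but a weaker choice. It matches the weighted estimate only without the country covariate, relies on equal variances across cells, and cannot be computed with an empty cell.

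The cost is a few sentences and a standard software option. The supplementary intervals become slightly wider: between no change and about 1.2 times in the settings simulated without a dose effect. The primary analyses do not change.

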5.4 Statistical Analysis Methods

5.4.1 Difference in Percentages

The difference in percentage, given by the difference between the proportion of subjects in the vaccine group, p_2 , with the event and placebo group, p_1 , with the event is calculated using the following formula:

$$\text{Difference in percentage} = (p_2 - p_1) * 100 = \left(\frac{E_2}{n_2} - \frac{E_1}{n_1} \right) * 100 \quad (1)$$

where E_1 and E_2 are the number of events in the placebo and vaccine groups respectively, and n_1 and n_2 are the number of subjects in the placebo and vaccine groups respectively with a valid assessment.

The 95% confidence intervals for the differences in percentages will be computed using the Miettinen and Nurminen (MN) [2] method. The following formula is used for the MN CI:

$$\text{MN CI} = \left((\hat{p}_2 - \hat{p}_1) \pm Z_{1-\frac{\alpha}{2}} \sqrt{\lambda \left(\frac{\tilde{p}_2(1-\tilde{p}_2)}{n_2} + \frac{\tilde{p}_1(1-\tilde{p}_1)}{n_1} \right)} \right) * 100 \quad (2)$$

where \tilde{p}_1 and \tilde{p}_2 are the maximum likelihood estimators for p_1 and p_2 under the null hypothesis that $p_1 - p_2 = 0$ and $\lambda = \frac{n_1+n_2}{n_1+n_2-1}$ and α is the selected level of significance. All confidence intervals for the difference in percentages outlined in this SAP will be two-sided 95% confidence intervals, i.e. with $\alpha = 0.05$.

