7.5 Missing Data

7.5.1 Immunogenicity data

The reasons for having missing immunogenicity data are as follows:

- Study withdrawal prior to the blood draw (Visit 4)
- Non-evaluable samples, which may be as a result of a low volume of blood
- Blood draw outside of the permitted time window

For the primary and secondary immunogenicity estimands a principal stratum approach will be taken for the missing data. Therefore, a complete case (CC) analysis will be performed for these estimands based on the assumption that the data are missing completely at random. Immunogenicity results are not

expected to have any relationship with subject withdrawal from the study. Non-evaluable samples are expected to occur as a result of an issue with sample collection, storage, transportation, or analytical error and not due to the trial vaccine received. Blood draws outside of the permitted time window are expected to occur due to a planning or logistical error and won't be impacted by the trial vaccine received.

For the supplementary immunogenicity estimands a treatment policy approach will be applied to the missing data, using the assumption that any missing data would have been similar in subjects who had the same type of, and number of, trial vaccinations.

There are 4 different trial vaccine options that will be considered, they are:

- 1 placebo vaccination (t_1)
- 2 placebo vaccinations (t_2)
- 1 HIL-214 vaccination (t_3)
- 2 HIL-214 vaccinations (t_4)

To account for the missing data in this setting, inverse probability weighting [3] will be used. For this method, weights, relating to the probability of a subject having CC data, will be calculated for each of the 4 different trial vaccine options. A logistic regression model will be used to calculate the probability of having CC data, with one covariate that has 4 levels for the type of vaccine and the number of doses received.

The weights will be calculated in the following way:

$$w_i = \frac{1}{P(CC|\mathbf{t}_i)}$$

where \mathbf{t}_i describes the trial vaccine option the subject receives, as defined above.

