9.1.1.3 Analysis Methods

A primary immunogenicity estimand and a supplementary estimand will be created for all of the endpoints outlined in **Table 8**. Analyses will be completed for the subgroups defined in **Section 7.4**.

For the primary immunogenicity estimands a complete case analysis will be performed, meaning any subjects with missing data for the parameter of interest will be excluded from the analysis.

For the supplementary immunogenicity estimands for the primary endpoints the missing data will be accounted for by reweighting the estimates using the method of inverse probability weighting. See **Section 7.5.1** for more details.

For the binary primary immunogenicity endpoints a standard summary for the categorical outcome will be presented as well as descriptive statistics for the continuous values. Further, the difference in percentage of subjects in the vaccine group with the event and the percentage of subjects in the

placebo group with the event will be evaluated. This will be presented along with a 95% CI calculated using the Miettinen and Nurminen [2] method as shown in **Section 5.4.1**.

For all continuous primary immunogenicity endpoints the geometric mean titer/concentration (GMT/GMC) with 95% CIs and geometric standard deviation (GSD) will be calculated. The GMRs between the vaccine group and the placebo group along with a 95% CI will be calculated using the analysis of variance (ANOVA) model with natural logarithm of antibody titer/concentration as the response variable and trial arm as a factor. Where country is used as a covariate (see **Section 7.3**) the adjusted GMs will also be presented. Further details can be found in **Section 5.4.3**.

For all primary immunogenicity parameters a reverse cumulative distribution curve will be produced, with titer/concentration on the x-axis and the percentage of patients below the titer value on the y-axis. All graphs will contain the two vaccine groups which will be overlaid.

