9.2.1.3 Analysis Methods

For the secondary immunogenicity endpoints data will only be analysed for the patients receiving HIL-214.

A secondary immunogenicity estimand and a supplementary estimand will be created for all of the endpoints outlined in **Section 9.2.1.2**. Analyses will be completed for the two country subgroups only, defined in **Section 7.4**.

For the secondary immunogenicity estimands a complete case analysis will be performed, meaning any subjects with missing data for the parameter of interest will be excluded from the analysis.

For the supplementary immunogenicity estimands for the secondary endpoints the missing data will be accounted for by reweighting the estimates using the method of inverse probability weighting. See **Section 7.5.1** for more details.

For all binary secondary immunogenicity endpoints a standard categorical summary will be presented. SRR is defined in **Section 5.3.2.2**.

For all continuous secondary immunogenicity endpoints a standard continuous summary of the outcome will be presented alongside the GM and GMFR and their confidence intervals. Where country is used as a covariate (see **Section 7.3**) the adjusted GMs will also be presented.

For all secondary immunogenicity parameters a reverse cumulative distribution curve will be produced, with titer/concentration on the x-axis and the percentage of patients below the titer/concentration value on the y-axis. All graphs will present the two vaccine groups which will be overlaid.

Line graphs and boxplots summarizing the GMT for each trial vaccine group for the serotypes GI.1 and GII.4 will also be produced. These outputs will both have the visits of baseline and Visit 4 on the x-axis and the GMT on the y-axis, presenting data on the log scale.

Bar plots for seroresponse, with 95% CIs, will also be created with the results for placebo and HIL-214 stacked next to each other and separate sets of bars for the serotypes GI.1 and GII.4.

10 Safety Analyses

All safety analysis is defined in this section. Along with the following summaries, all safety endpoints will be listed by vaccine group. Where summaries are presented overall, after first dose and after second dose subjects will be summarised under the trial vaccine they receive for that period. If a subject receives HIL-214 for either dose they will be summarised under HIL-214 in the overall summary.

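### The supplementary weighted confidence intervals for binary endpoints count unmeasured infants as measured, so they are too narrow when results are missing

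*SAP*

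**What the plan says.** SAP 5.4.1 defines the standard MN interval. Its denominators n1 and n2 "are the number of subjects in the placebo and vaccine groups respectively with a valid assessment", and the same n enters lambda.

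SAP 7.5.1 rewrites this for the supplementary (treatment-policy) estimands. The probability of having a result comes from a logistic model "with one covariate that has 4 levels for the type of vaccine and the number of doses received". Each arm's weighted events are divided by N1 or N2, which "are the number of subjects in the analysis set in the placebo and vaccine groups respectively". That set is the immunogenicity full analysis set (SAP 7.1 and 7.2). Membership requires at least one in-window trial-vaccine dose, not a Visit 4 result. The interval is then written with N1 and N2 in both variance terms and in lambda, and "the reweighted proportions will be used in the calculation of the confidence intervals".

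For the one-arm intervals, "Clopper-Pearson CIs will be calculated using the exact weight-adjusted values using the Beta distribution"; the denominator is not named. One case is explicit: "If all observed cases are positive the number of events will be set to" N1 and N2. If every observed infant in both arms is positive, no MN interval is produced. If one-dose data are too sparse, the groups are pooled to one weight per arm.

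The main analyses differ. SAP 9.1.1.3 states: "For the primary immunogenicity estimands a complete case analysis will be performed".

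**The concern.** The precision of a proportion depends on how many infants were measured. An interval built on N treats infants without a Visit 4 result as if they had one, and it understates uncertainty by more as more results are missing. The SAP gives no robust, bootstrap or effective-sample-size variance to offset this.

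The two-arm intervals affected are those for diphtheria, tetanus, polio, PRP and HBsAg. SAP 7.4 reports these by country only, so the arms are smaller than 200. The trial is descriptive, so readers will judge interference from the intervals. A supplementary interval that looks tight partly because unmeasured infants were counted could be read as added reassurance.

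**Working it through.** The plan states no interval width or missing rate, so there is no figure to reproduce.

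**Inputs.** Two-sided 95% intervals, z = 1.96 (SAP 5.4.1). About 400 infants randomised 1:1 (SAP 6), at least 100 of them in the US (Protocol 4.2). Assumed arm sizes within country: 50 (100/2) and 150 (300/2). Assumed missing: 5%, 10%, 20%.

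**Point estimate.** The weight model has one level per vaccine-by-dose group, so each weight is N_i/n_i and the weights sum to N. Dividing weighted events by N is therefore correct if weights and N refer to the same infants. With one weight per arm, p = E × (N/n) / N = E/n, the complete-case value.

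**Interval width.** The half-width in SAP 7.5.1 is 1.96 × sqrt(lambda × p̃(1−p̃) × (1/M1 + 1/M2)), with p̃ the pooled proportion and M = N. Using M = n gives the interval the data support. With equal arms and equal completeness the ratio is sqrt(n/N):

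- 5% missing: sqrt(0.95) = 0.975
- 10% missing: sqrt(0.90) = 0.949
- 20% missing: sqrt(0.80) = 0.894

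The variance denominators drive this. Lambda contributes about 0.03% of width (400/399 against 320/319).

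**Examples, N = 50 per arm (placebo vs HIL-214, difference in points).**

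- 43/45 vs 41/45: half-width 9.8 with M = 50, giving −14.3 to 5.4; 10.4 with M = 45, giving −14.8 to 5.9.
- 38/40 vs 36/40: half-width 10.4 with M = 50, giving −15.4 to 5.4; 11.6 with M = 40, giving −16.6 to 6.6.

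**Coverage.** Exact enumeration of both binomials, no true difference, SAP formula as written. Outcomes with no interval (all positive in both arms) are counted as covered.

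| N per arm | Measured | With N, at rates 90/95/97% | With n |
|---|---|---|---|
| 150 | 135 | 93.8/94.1/93.3% | 95.2/95.2/95.6% |
| 150 | 120 | 91.9/91.7/93.0% | 95.0/95.4/95.6% |
| 50 | 45 | 94.0/95.1/97.5% | 95.2/95.9/97.7% |
| 50 | 40 | 91.3/90.7/92.9% | 94.1/95.7/98.1% |

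Leaving out the no-interval outcomes changes little: at 97%, 45 of 50 goes from 97.5% to 97.4%, and 40 of 50 from 92.9% to 92.3%.

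**All-positive Clopper-Pearson.** The lower limit is 0.025^(1/M).

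- N = 50: 92.9% by the SAP rule; 92.1% with 45 measured; 91.2% with 40.
- N = 150: 97.6% by the SAP rule; 97.3% with 135 measured; 97.0% with 120.

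**Clopper-Pearson otherwise.** If N is also the denominator here, coverage averaged over rates from 50% to 99% is 95.9% (45 of 50), 95.1% (135 of 150), 94.6% (40 of 50) and 93.6% (120 of 150).

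**Two weights in an arm (assumed example).** Take 142 two-dose infants, 134 measured, and 8 one-dose infants, 4 measured. The weights are 142/134 and 8/4 = 2. Their sum is 150; the sum of squares is 142²/134 + 4 × 2² = 150.48 + 16 = 166.48. The effective sample size is 150²/166.48 = 135.2, so the SAP width is sqrt(135.2/150) = 0.949 of the width it should have. Simulated coverage at a 90% rate (400,000 runs) is 93.7% with N, 94.7% with n = 138 and 95.0% with 135.2. With 130 of 142 and 4 of 8 measured, and rates of 90% and 80% in the two dose groups, it is 93.1%, 94.6% and 94.8%.

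**The case against.** The reading of SAP 7.5.1 is not in dispute; the size is.

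- **High response rates.** The all-positive rules show that near-complete response is expected. At a true rate of 99%, the N-based formula covers 97.4% (135 of 150), 97.9% (120 of 150), 99.9% (45 of 50) and 99.0% (40 of 50). This stands: the intervals are still narrower than n supports, but they do not under-cover there.
- **Fixed counts at 50 per arm.** Part of the shortfall comes from fixing exactly 40 measured. With infants missing at random at 20%, simulated coverage at 90/95/97% is about 91.9/92.7/95.4%. This also stands. At 150 per arm the shortfall remains: about 93.5 to 93.7% at 10% missing and 92.0 to 92.3% at 20%.
- **Low missingness.** At 5% missing at random, coverage is about 94.3 to 94.5% at 150 per arm and 94.3/95.0/97.3% at 50. That is practically harmless, and the documents do not say which rate applies.
- **A narrower supplementary interval may be legitimate.** The full analysis set admits infants with missed or out-of-window doses, so it can contain more measured infants than the primary set. This is right: a narrower interval is not by itself proof of the error.
- **Low stakes.** Only supplementary binary intervals are touched, and no success rule depends on them.

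These points limit the consequence. None justifies using N as the sample size.

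**Conclusion.** The concern holds and should be fixed. As written, the supplementary MN intervals are too narrow by the factor sqrt(n/N) when there is one weight per arm and completeness is equal: 5.1% at 10% missing and 10.6% at 20%. At 150 per arm with 20% missing and true rates of 90% to 97%, nominal 95% coverage falls to about 92 to 93%. The loss is small at 5% missing, may be absent at 50 per arm with 10% missing, and was absent in every 99%-rate case above. All of this rests on assumed missing rates, arm sizes and response rates.

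The Clopper-Pearson effect is smaller. It is explicit only in the all-positive case, where the lower limit moves by 0.3 to 0.6 points at N = 150 and 0.8 to 1.7 at N = 50. It is the only part that reaches norovirus seroresponse, because SAP 9.2.1.3 says "For the secondary immunogenicity endpoints data will only be analysed for the patients receiving HIL-214", and that interval is conservative to begin with. The weighted point estimate and the primary and secondary complete-case intervals are not affected.

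**What to change.** In SAP 7.5.1, keep the weighted proportion p, divided by N, and change only the intervals:

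1. In the MN variance and lambda, replace N1 and N2 by each arm's effective sample size, n_eff = (Σw)² / Σw², summed over measured infants. With one weight per arm this equals the number measured.
2. Compute Clopper-Pearson from p × n_eff events out of n_eff; the Beta form accepts non-integers.
3. When all observed infants are positive, use n of n, the number measured.
4. As a clarification, state that weights and N are both taken within country where results are reported by country.

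A robust or bootstrap variance would also be defensible, and plain n removes most of the error. n_eff is itself approximate when one-dose and two-dose infants respond at different rates (94.8% in the example above).

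The cost is SAP wording and programming, with no new data. With one weight per arm, supplementary MN intervals widen by about 5.4% at 10% missing (1/0.949) and 11.8% at 20% (1/0.894).
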